#### Statistical methods:

The primary endpoint is the rate of investigator-confirmed HAE attacks during dosing in the entire treatment period of Part 1, expressed as attacks per month where 1 month is defined as 28 days. Comparisons of the rate of investigator-confirmed HAE attacks between each BCX7353 dose and placebo during the entire dosing period for Part 1 will be conducted using a Poisson regression model. The number of investigator-confirmed attacks will be included as the dependent variable, the treatment will be included as a fixed effect, baseline attack rate will be included as a covariate and the logarithm of duration on treatment will be included as an offset variable. The estimated monthly rate of attacks for each treatment group, the treatment differences expressed as the attack rate ratio (BCX7353 over placebo rate ratio) and their associated 95% confidence intervals (CIs) will be provided from the Poisson regression model.

Missing data sensitivity will be conducted for the analysis of the primary endpoint using data collected post treatment discontinuation and using multiple imputation for missing data, In addition, a a tipping point analysis will be conducted. A separate analysis using only data from subjects who completed Part 1 will also be conducted.

Analysis of secondary endpoints for Part 1 will be as follows:

Treatment comparisons in the AE-QoL total score change from baseline will be analyzed using a mixed model for repeated measures (MMRM) with fixed effects for treatment, baseline attack rate, baseline AE-QoL, visit, a visit by treatment interaction, and a random effect for subject. An unstructured covariance structure will be used. The estimated treatment difference for each BCX7353 dose vs. placebo at each visit will be displayed together with the 95% CI and the associated p-value. Primary inferences will be drawn from treatment differences for the changes from baseline derived from the MMRM model at Week 24. The change from baseline in the AE-QoL domain scores (function, fatigue, nutrition, and fear/shame) will also be analyzed using the MMRM model.

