# 2. INTRODUCTION

The purpose of this statistical analysis plan (SAP) is to describe the planned analyses and data displays to be included in the Clinical Study Report (CSR) for Study BCX7353-302.

Protocol Revision Chronology:								
Protocol	21 November 2017	Version 1						
Protocol	11 October 2018	Version 2 – added Part 3 to extend the study to 96 weeks to allow for collection of long-term safety and effectiveness data.						

This SAP was developed in accordance with the International Council for Harmonisation (ICH) E9 guideline. The purpose of this document is to provide details on the statistical methodology used to analyze the safety and efficacy data for Study BCX7353-302. Study population definitions, derivations of variables, handling of missing data, and other information necessary for analysis of study data are provided. Planned tables, figures, and listings are specified. All decisions regarding final analysis will be made, the SAP will be finalized, approved by the Sponsor, and placed on file before the database is locked for interim analysis.

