# 8.6. Analysis of the Primary Efficacy Endpoint

## 8.6.1. Primary Efficacy Analysis

The primary efficacy endpoint for Part 1 of the study is the rate of investigator-confirmed HAE attacks during dosing in the entire 24-week treatment period during Part 1 (Day 1 to first dose of Part 2). The first dose in Part 2 is expected on Day 169. The primary efficacy analysis will be produced using the ITT population. The estimand will be based on data from subjects who are on study treatment and this analysis will not include data post treatment discontinuation.

The number of investigator-confirmed HAE attacks for Part 1 will be analyzed by treatment group using appropriate descriptive statistics for the confirmed attack rate (expressed as attacks/month) based on the 24-week dosing period or until study treatment discontinuation, if applicable. An additional summary of confirmed attack rate by month, including change from baseline attack rate and percentage change from baseline attack rate by month, will be produced. The primary efficacy analysis will be conducted using Part 1 data and the primary efficacy endpoints will be summarized and listed by Part 1 treatment group.

The attack rate and the treatment comparisons between each BCX7353 dose and placebo in the rate of investigator-confirmed HAE attacks during the Part 1 dosing period will be analyzed using a Poisson regression model. The number of investigator-confirmed attacks will be included as the dependent variable, the treatment will be included as a fixed effect, the stratification variable (baseline attack rate) will be included as a covariate and the logarithm of duration on treatment will be included as an offset variable. The estimated rate of attack for each treatment group, the treatment differences expressed as the attack rate ratio (BCX7353 over placebo rate ratio) and their associated 95% confidence intervals (CIs) will be provided from the Poisson regression model. The percentage reduction from placebo will be calculated for each dose as:

Rate reduction = 
$$1 - \text{attack rate ratio} = 1 - \frac{R_A}{R_P}$$

Where  $R_P$  is the estimated attack rate for Placebo treatment and  $R_A$  is the estimated attack rate for Active treatment.

Example SAS pseudo-code for the Poisson regression analysis is as follows:

```
proc genmod data = datasetname;
class trt01p catblatk/param=glm;
model icattacks = trt01p catblatk /dist=poisson link=log offset=logdurtrt;
run;
```

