All statistical tests will be 2-sided. Multiplicity adjustments for Part 1 analyses for the 2 dose groups are discussed in Section 8.5 along with handling of testing of multiple endpoints.

The Poisson model assumes that the mean and variance are equal. When the variance in the data is larger than the mean, the model is said to be over-dispersed. Over-dispersion is more likely to be a problem if a significant number of subjects have no attacks during the 24-week treatment period. As a sensitivity analysis to examine the appropriateness of the Poisson model, a negative binomial model will be used in place of the Poisson regression model. When the negative binomial dispersion parameter is equal to zero, the negative binomial and Poisson models are equivalent. If the results of the model obtained using the negative binomial distribution are similar to that of the model that assumes the Poisson distribution and a statistical test of the dispersion parameter does not show that it is significantly greater than zero, the Poisson model will remain as the primary model for analysis.

Plots of mean confirmed attack rate by month and scatter plots of baseline attack rate vs. 24-week attack rate will be produced with a different color for each treatment. Plots of mean attack rate per month will be updated to include the Part 2 data at the end of the study. Adjusted subject-reported attack rate data per month will be plotted separately for Part 3, as Part 3 does not include investigator confirmation of attacks.

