# 8.7.3. Rate of Investigator-Confirmed HAE Attacks during Dosing in the Effective Treatment Period

The rate of investigator-confirmed HAE attacks during dosing in the effective treatment period is a secondary endpoint for Part 1.

Summaries and analysis of the investigator-confirmed attack rate using the ITT population for the effective treatment period (Day 8 through Week 24, inclusive) will be conducted using Poisson regression, similar to what is done for the primary efficacy endpoint analysis.

Summary displays will be updated at the end of Part 2 to include data collected during Part 2 of the study. For subjects originally randomized to placebo, data on active treatment will be summarized using the adjusted visits.

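### SAP 8.6.1 makes the Poisson primary model conditional on a dispersion check but never says which model is primary if the check fails, and endpoint 4 has no clear rule at all

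*SAP*

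**What the plan says.** The Technical Summary (Statistical methods) compares each dose with placebo during "the entire dosing period for Part 1 will be conducted using a Poisson regression model". Section 8.6.1 repeats this: the rate of confirmed "HAE attacks during the Part 1 dosing period will be analyzed using a Poisson regression model". Its pseudo-code requests a Poisson distribution with a log link and a log-duration offset, and has no scale or robust-variance option.

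Later in 8.6.1 the SAP recognises that the variance may exceed the mean. As a sensitivity analysis, "a negative binomial model will be used in place of the Poisson regression model". Two conditions follow, joined by *and*: the NB results resemble the Poisson results, and "a statistical test of the dispersion parameter does not show that it is significantly greater than zero". If both hold, "the Poisson model will remain as the primary model for analysis". The paragraph has no *otherwise* clause. The same section states that "All statistical tests will be 2-sided".

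For endpoint 4 (attack rate from Day 8), Section 8.7.3 says the analysis "will be conducted using Poisson regression, similar to what is done for the primary efficacy endpoint analysis".

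Section 5.2 places unblinding after the database freeze for the Part 1 analysis. Section 2 says: "All decisions regarding final analysis will be made, the SAP will be finalized, approved by the Sponsor, and placed on file", before the lock for the interim analysis.

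**The concern.** A Poisson model sets the variance equal to the mean. If subjects differ in their underlying attack rates beyond what the covariate explains, its standard errors are too small and its p-values too low. The SAP names this risk and names the usual remedy, but does not finish the rule. It leaves out the measure of similarity, the dispersion test and its level, and the model that becomes primary when Poisson is not kept.

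Comparing treatment results between two models needs treatment codes, so the check falls after the freeze, when both sets of p-values are visible. The primary p-values drive the Hochberg steps and the hierarchy in Section 8.5. A dose with little or no effect that is wrongly declared effective on endpoint 1 would carry its testing forward to the secondary endpoints.

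**Working it through.** **Is the gap filled elsewhere?** The NB analysis is absent from the sensitivity analyses in 8.6.2, from the changes in Section 15 and from the planned table titles in Section 17.1. Section 2 states an intention to decide everything before lock but supplies no rule.

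**The plan's own figure.** Section 4.3.1 gives 94% power with 32 per arm, difference 0.5, SD 0.55, two-sided 0.05. The normal approximation gives Φ(0.5/(0.55·√(2/32)) − 1.96) = 95.3%, and the noncentral t gives 94.7%. With 20% dropout, 32/0.8 = 40. The figures reproduce, but this is a two-means calculation and does not test the Poisson variance.

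**How large might overdispersion be?** Inputs from 4.3.1: a difference of 0.70 attacks/week, equal to a 73.8% reduction, and a pooled SD of 0.55 over Days 8 to 28 (3 weeks).
- Placebo rate: 0.70/0.738 = 0.9485/week. Active (125 mg): 0.9485 − 0.70 = 0.2485/week.
- The SD must be per week. Per 28 days, the Poisson minimum SD of a 21-day rate would be √(4 × 0.9485/0.75) = 2.25 on placebo and √(4 × 0.2485/0.75) = 1.15 on active, both above 0.55.
- With placebo weight w in the pooled variance, k = [0.55² − (w·0.9485 + (1−w)·0.2485)/3] / [w·0.9485² + (1−w)·0.2485²], and the 24-week placebo variance/mean is 1 + k·0.9485·24.

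| w (assumed) | k | variance/mean |
|---|---|---|
| 1/3 | 0.42 | 10.5 |
| 1/2 | 0.21 | 5.9 |
| 3/4 | 0.065 | 2.5 |
| 0.9 | 0.012 | 1.3 |
| 0.95 | about 0 | about 1 |

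The SAP does not state the weights or which arms were pooled.

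**Effect on Type I error.** Without covariates, the two-sided Poisson error is 2·(1 − Φ(1.96/√φ)), where φ = 1 + 24rk and r is the weekly rate (assumed range 0.25 to 0.95).
- k = 0.05, r = 0.25: φ = 1.30, error 8.6%.
- k = 0.21, r = 0.95: φ = 5.79, error 41.5%.

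A null simulation used 2,000 trials per setting, three arms of 40, 24 weeks, no dropout, gamma heterogeneity, a 6-week run-in with at least 2 attacks, and a likelihood-ratio dispersion test at two-sided 5%. *Similar* was ignored because it is undefined.

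| k | Poisson error, two-level baseline | Poisson error, log baseline rate | Dispersion significant, two-level baseline |
|---|---|---|---|
| 0.02 | 7-11% | 7-10% | 10-75% |
| 0.05 | 9-17% | 9-16% | 39-100% |
| 0.10 | 11-26% | 11-22% | 84-100% |
| 0.21 | 16-39% | 15-28% | 100% |

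NB error was 5-6% throughout, and 5-7% under the SAP rule read with an NB fallback. A smaller run (400 null trials per setting, k 0.05 to 0.21) gave 9-40% for Poisson and about 5-10% for NB, with more simulation noise.

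**Effect on decisions.** Dispersion was significant and the models disagreed in 0-0.2% of comparisons at the planned 50% reduction (40 per arm), and in 4-18% at a 25% reduction, which the SAP does not plan for. At k = 0.02 a separate check gave under 1% disagreement at 25%.

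**The case against.** The strongest reply is that the rule is nearly complete. The two conditions are joined by *and*, so Poisson is kept only if both hold, and NB is the only other model named. Followed that way, Type I error is 5-7%, and the large Poisson errors arise only if Poisson is reported against the rule's own condition. This stands as an account of what a careful analyst would do. It does not supply the missing sentence: one reader can cite the primary-model statement for Poisson, and another can cite the dispersion paragraph for NB.

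It can also be said that *similar* matters little. That is right. It can bind only when dispersion is not significant, and the models then nearly coincide. In a check without covariates (500 trials per setting), significance decisions then differed in at most 1.2% of null comparisons, at most 2.4% at a 25% reduction, and none at 50%.

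Timing alone is not the defect either. A dispersion test from a model with treatment terms also needs treatment codes. What protects the analysis is a rule fixed beforehand.

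A reader might infer heavier overdispersion from the planning assumption (placebo mean 1, SD 0.55) by taking 0.55 as a 24-week SD. Then 0.55² × 24r gives variance/mean of 1.8, 3.6 and 6.9 at 0.25, 0.5 and 0.95/week, with simulated Poisson errors of 13%, 26% and 42%. The documents do not support this. The SD comes from 21 days, over which pure Poisson counts have a coefficient of variation of 1/√(3r) = 1.15, 0.82 and 0.59 at those rates, all above 0.55. Those figures should not be used.

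**Conclusion.** The gap is real and should be fixed. The SAP withdraws its support for Poisson under stated conditions without making NB primary. For endpoint 4 it specifies Poisson and carries the dispersion rule over, if at all, only through a reference to similarity with the primary analysis.

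The size is conditional. Overdispersion is plausible, but the Study BCX7353-203 figures allow anything from k about 0.42 to none, on weights that are not stated. Over k = 0.05 to 0.21 and 0.25 to 0.95 attacks/week, reporting Poisson would give roughly 9-40% error per comparison, against about 5-7% with NB or an NB fallback.

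A reader might infer that the main result is at risk under the planned effect. It is not: at a 50% reduction the models almost always agree. The exposure is a weak or null dose, and one such dose among the two is enough.

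One limit remains. The supplied protocol is for Study BCX7353-202 and the SAP is for BCX7353-302, so whether the matching protocol states the fallback cannot be checked.

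**What to change.** Before unblinding, name NB regression (log link, log-duration offset, same terms) as the primary model in 8.6.1 and 8.7.3. Make Poisson the sensitivity analysis, and the reported model if the dispersion estimate is zero, where 8.6.1 itself says the two are equivalent. Delete the sentence that keeps Poisson as primary.

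Minimum alternative: state that NB is primary for endpoints 1 and 4 whenever a likelihood-ratio test of zero dispersion is significant at a stated level and sidedness, and Poisson otherwise. If the test is one-sided, record it as an exception to the two-sided rule. Delete the similarity condition.

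The cost is one or two sentences, one option in the code, and somewhat wider intervals when counts are overdispersed. Power for the planned 50% reduction is Φ(log 2/SE − 1.96), with SE = √((1/m₀ + 1/m₁ + 2k)/n), m₀ = 24r and m₁ = m₀/2. At 32 per arm and 0.25/week, the least favourable rate used, k = 0.21 gives SE 0.170 and power 98.3%; k = 0.42 gives SE 0.205 and power 92%. With 40 per arm these become 99.5% and 97%. At a 25% reduction (k = 0.21, 0.5/week, two-level baseline), NB power is 76% against 93% for Poisson, but Poisson's Type I error there is 26%. With no overdispersion NB costs almost nothing: error 4.3% against 4.5%.

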#### **3.2.7.** Part 2 Secondary Endpoints

- Number and rate of HAE attacks
- Durability of response (attack rate trend over time)
- Number and proportion of days with angioedema symptoms
- Use of HAE attack medications
- Discontinuations due to lack of efficacy
- Durability in angioedema QoL questionnaire scores
- Durability in EQ-5D-5L scores
- Durability in TSQM scores
- Durability in WPAI scores

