### 6.7.5. Derived Efficacy Endpoints

#### 6.7.5.1. Attack Rate

#### **General Formula for Attack Rate**

In general, the formula for computing an attack rate is the number of attacks meeting the attack criteria divided by the duration of treatment during the reporting period of interest.

duration of treatment during the reporting period of interest = the last day in the reporting period - the first day in the reporting period + 1

Attack Rate 
$$\left(\frac{attacks}{month}\right)$$
 During Reporting Period of Interest  
=  $\frac{\text{Number of Attacks * 28}}{\text{Duration of Treatment During Reporting Period in Days}}$ 

If the subject discontinues treatment early, any attacks that occur within 24 hours after last dose will be counted in the calculation of attack rate and the additional 24 hour period will be included in the duration of the reporting period.

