#### **Confirmed Attack Rate**

Confirmed attack rates will be computed based on the number of confirmed attacks that occur during the reporting period of interest.

Confirmed attack rates will be computed for the following reporting periods and expressed in units of attacks/month where 1 month = 28 days:

- Parts 1 and 2, By month
- Parts 1 and 2, Entire dosing period
- Parts 1 and 2, Effective dosing period

Confirmed attack rates will be computed for Part 1 and at the end of Part 2. For confirmed attack rates by month, months will be defined in blocks of 28 days, beginning on Day 1, the day of first dose. The entire dosing period begins on Day 1 or adjusted Day 1 during Part 2 for subjects originally randomized to placebo. The effective dosing period similarly begins on Day 8 or adjusted Day 8. Part 1 continues until the time of Part 2 dose. Part 2 continues until the time of first dose for Part 3. Investigator confirmation is not done in Part 3 and so confirmed attack rate

will not be computed for Part 3. If the subject discontinues treatment early, the reporting period will continue through 24 hours post last dose and any attacks that occur within 24 hours after last dose will be counted in the calculation of attack rate. If there are confirmed attacks in the eCRF without corresponding diary information, as may happen if a subject verbally reports an attack to an investigator but does not enter it into the ediary, the attack will be counted.

For sensitivity analyses for missing data for the Part 1 primary analysis, confirmed attack rates for the entire dosing period for subjects who discontinue treatment early will be re-computed as a weighted average of the observed post-treatment discontinuation attack rate and an imputed attack rate for periods of missing data post-treatment discontinuation. Details are provided in Section 6.8.1.

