# Table 13:Reason for Study Treatment Discontinuation and Whether Data are
Considered Missing at Random or Not

Missing Data Considered Missing at Random	Missing Data Considered Not Missing at Random
Subsequent determination that inclusion/exclusion criteria were not met	Laboratory abnormality or adverse event
Intercurrent illness or emergence of new illness/medical condition/pregnancy	Discontinuation due to QT prolongation
Subject noncompliance with study drug or procedures	Discontinuation due to rash
Subject withdrew consent	Perceived lack of efficacy
Other a	Other a
Sponsor discontinuation a	Sponsor discontinuation a
Investigator judgment a	Investigator judgment a

a A review of discontinuations for Sponsor discontinuation, Investigator judgment, or other reason will be completed prior to unblinding of Part 1 data for determination of missing at random or not missing at random.

1. A tipping point analysis will be conducted using the observed data post treatmentdiscontinuation combined with imputed data for missing time periods. However, for tipping point analysis,  $r_{imputed}$  will be multiplied by a factor,  $\delta$ , for the active treatment group in the determination of the analyzed rate, as shown below. For the placebo group, there will be no such multiplicative factor. The tipping point is the value of  $\delta$  that leads to a reversal of a significant p-value. It shows how much larger than expected the attack rate would need to be for the time period of missing data for the active group in order to "tip" the significance level to non-significant. For tipping point analysis, the analyzed rate for the active treatment group is:

 $r_{analyzed} = f * r_{observerd} + (1 - f) * \delta * r_{imputed}$ 

For the placebo group, the analyzed rate would remain as:

 $r_{analyzed} = f * r_{observerd} + (1 - f) * r_{imputed}$ 

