## 8.7. Analysis of the Secondary Efficacy Endpoints

#### 8.7.1. Angioedema Quality of Life (Total and Domain Scores)

Change from baseline in AE-QoL questionnaire at Week 24 (total score) is a secondary endpoint for Part 1. Durability in AE-QoL questionnaire scores is a secondary endpoint for Parts 2 and 3.

The actual and change from baseline domain and total scores will be summarized by visit and treatment. For Part 1, changes from baseline in AE-QoL will be assessed with a MMRM model with fixed effects for treatment, baseline attack rate, baseline AE-QoL, visit, and a visit by treatment interaction and a random effect for subject. An unstructured covariance structure will be used. The estimated treatment difference comparing each active treatment to placebo at each post-baseline visit (Weeks 4, 6, 12, 18, and 24) will be displayed together with the 95% CI and the associated p-value. Least squares means (LSM) for each visit will also be presented with the standard error and the number of subjects contributing to the LSM. Total and domain scores will be listed for each subject and visit. The responses to the individual AE-QoL questions will also be listed.

Figures of mean actual and change from baseline AE-QoL total and domain scores will be produced with 1 line per treatment group. In addition, a cumulative distribution plot of AE-QoL Total Score at Week 24 will be provided.

Final analyses at the end of study will also include data from visits at Weeks 28, 32, 36, 48, 60, 72, 84, 96, and follow-up. Summaries will be updated to include the additional information. An additional descriptive summary of change from Week 24 will be provided for Part 2 and 3 visits for subjects originally randomized to placebo treatment.

A summary and analysis of the number and percent of subjects with at least a 6-point decrease (Minimum Clinically Important Difference [MCID]) in total AE-QoL score will be performed by visit for Part 1. The summary will be repeated at the end of the study. The analysis for Part 1 will be based on a logistic model with response of achievement of the MCID (yes/no), baseline attack rate and baseline AE-QoL total score as covariates and a fixed effect for treatment.

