14.2.1.18	ITT	Summary of Rate of Subject-Reported Attacks During Part 1
14.2.1.18.ES	ITT	Summary of Rate of Subject-Reported Attacks During Entire Study
14.2.1.18.P3	ITT	Summary of Rate of Subject-Reported Attacks During Part 3
14.2.1.19.P3	ITT	Summary of Rate of Subject-Reported Attacks Requiring Treatment During Part 3
14.2.2.1	ITT	Summary of Rate of Investigator-Confirmed Attacks By Month During Part 1
14.2.2.1.ES	ITT	Summary of Rate of Investigator-Confirmed Attacks By Month During Entire Study
14.2.2.1.P3	ITT	Summary of Rate of Investigator-Confirmed Attacks By Month During Part 3
14.2.3.1.1	ITT	Summary of AE-QoL Scores, Part 1
14.2.3.1.1.ES	ITT	Summary of AE-QoL Scores, Entire Study
14.2.3.1.2	PP	Summary of AE-QoL Scores, Part 1
14.2.3.1.2.ES	PP	Summary of AE-QoL Scores, Entire Study
14.2.3.2	ITT	Summary of AE-QoL Scores, Part 1 by Subgroups
14.2.3.7	ITT	Number and Percent of Subjects Achieving the MCID (Decrease in Total AE-QoL Score), Part 1

Output #	Population	Output Title
14.2.3.7.ES	ITT	Number and Percent of Subjects Achieving the MCID (Decrease in Total AE-QoL Score), Entire Study
14.2.4.1	ITT	Summary of Number and Proportion of Subjects Who are Investigator-Confirmed Attack-Free, Part 1
14.2.4.1.ES	ITT	Summary of Number and Proportion of Subjects Who are Investigator-Confirmed Attack-Free, Entire Study
14.2.4.2	ITT	Summary of Number and Proportion of Subjects Who are Subject-Reported Attack-Free, Part 3
14.2.4.3	ITT	Summary of Number and Proportion of Subjects Who are Investigator-Confirmed Attack-Free in the Effective Dosing Period, Part 1
14.2.4.3.ES	ITT	Summary of Number and Proportion of Subjects Who are Investigator-Confirmed Attack-Free in the Effective Dosing Period, Entire Study
14.2.5.1.1	ITT	Summary of Number and Proportion of Days with Angioedema Symptoms from Investigator- Confirmed Attacks, Part 1
14.2.5.1.1.ES	ITT	Summary of Number and Proportion of Days with Angioedema Symptoms from Investigator- Confirmed Attacks, Entire Study
14.2.5.1.1.P3	ITT	Summary of Number and Proportion of Days with Angioedema Symptoms from Subject-Reported Attacks, Part 3
14.2.5.1.2	РР	Summary of Number and Proportion of Days with Angioedema Symptoms from Investigator- Confirmed Attacks, Part 1
14.2.5.1.2.ES	РР	Summary of Number and Proportion of Days with Angioedema Symptoms from Investigator- Confirmed Attacks, Entire Study
14.2.5.1.2.P3	РР	Summary of Number and Proportion of Days with Angioedema Symptoms from Subject-Reported Attacks, Part 3

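### Study 302 SAP: durability of response rests on monthly mean attack rates among subjects still on drug, which response-related drop-out can shift with no change within subjects

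*SAP*

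**What the plan says.** Only the SAP bears on this point, because the protocol supplied is for Study 202.

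- **Endpoint.** Section 3.2.7 lists "Durability of response (attack rate trend over time" among the Part 2 secondary endpoints, and Section 3.2.9 repeats it for Part 3. No section gives it a model. Section 8.1 makes Part 2 descriptive and rules out hypothesis tests in Parts 2 and 3.
- **Displays.** Section 8.6.1 states "Plots of mean attack rate per month will be updated to include the Part 2 data at the end of the study", with Part 3 plotted separately. The matching table is 14.2.2.1.ES, "Summary of Rate of Investigator-Confirmed Attacks By Month During Entire Study", labelled ITT. Section 8.6.1 also specifies by-month change and percentage change from baseline, but in its description of the Part 1 analysis.
- **How each rate is formed.** Section 6.7.5.1 defines a rate as "the number of attacks meeting the attack criteria divided by the duration of treatment during the reporting period of interest". For the monthly version, "months will be defined in blocks of 28 days, beginning on Day 1, the day of first dose". On early stopping, "If the subject discontinues treatment early, the reporting period will continue through 24 hours post last dose". The Part 3 rate follows the same 24-hour rule.
- **Drop-out.** Table 13 puts "Perceived lack of efficacy" among the reasons treated as not missing at random. The use of post-discontinuation data, the imputation and the tipping-point analysis (Sections 6.8.1 and 8.6.2) apply to the Part 1 primary endpoint. The completers population (Section 6.5.5) is for Part 1 only.
- **AE-QoL.** Section 8.7.1 says "Durability in AE-QoL questionnaire scores is a secondary endpoint for Parts 2 and 3" and plans by-visit summaries. Change from Week 24 is planned only for subjects first randomized to placebo.

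**The concern.** A subject who stops drug contributes nothing to any later month, despite the ITT label on the table. The average at month 12 is therefore taken over a different set of people from the average at month 1. If poorer responders are more likely to go, the mean falls as they go even when nobody's rate has changed, and a real loss of response in those who stay can be offset and plotted as flat.

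The Part 2 and 3 objectives ask about attack frequency over 24 to 48 and 48 to 96 weeks, and these curves are what a reader will look at for the answer. Section 5.1 adds that by-month attack rates and by-visit AE-QoL after Week 24 may be produced at a data cut made for regulatory filings. The SAP recognises that leaving can be informative, but it carries that recognition no further than Part 1.

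**Working it through.** **Inputs (SAP Section 4.3.1).** Placebo rate 1 unit; 50% reduction, so active rate 0.5; SD 0.55; 32 per group; drop-out allowance 20%.

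**Reproducing the SAP's own figures.** With 32 per group, difference 0.5, SD 0.55 and two-sided 0.05, power is 95.3% by the normal approximation and 94.7% by the t test on 62 df; the SAP states 94%. The inflated size is 32/(1 − 0.20) = 40, as stated. The SAP gives no figure for durability.

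**Composition effect with every subject's rate constant.** Let d be the share who leave and r their mean rate. The mean among those who stay is (0.5 − d·r)/(1 − d). The false change is that mean divided by 0.5, minus 1. The true rise in stayers that would plot as flat is 0.5 divided by that mean, minus 1. The values of d and r below are assumptions, except that 20% is the SAP's allowance.

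| d | r | Mean of stayers | False change | Rise plotted as flat |
|---|---|---|---|---|
| 0.20 | 1.00 | (0.5 − 0.20)/0.8 = 0.375 | −25% | 33% |
| 0.20 | 0.75 | (0.5 − 0.15)/0.8 = 0.4375 | −12.5% | 14% |
| 0.10 | 1.00 | (0.5 − 0.10)/0.9 = 0.444 | −11% | 12.5% |
| 0.20 | 0.50 | (0.5 − 0.10)/0.8 = 0.500 | 0% | none |

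**Graded dependence, by simulation.** Subject rates follow a gamma distribution with mean 0.5 and stay constant over twelve 28-day months. The between-subject SD is 0.37 or 0.55. The lower value takes Poisson noise over the three-week period behind the SAP's SD out of 0.55, reading units as attacks per week: √(0.55² − 0.5/3) = 0.37. Total drop-out is 20%, and the monthly hazard of leaving rises with the subject's own rate. The table gives the change in the on-treatment mean from month 1 to month 12, for SD 0.37 and 0.55.

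| Hazard ratio of leaving per SD of rate | No true change | Every subject worsens by 15% |
|---|---|---|
| 1 | 0%, 0% | +15%, +15% |
| 1.5 | −8%, −13% | +6%, +1% |
| 2 | −14%, −21% | −1%, −9% |
| 3 | −19%, −29% | −7%, −18% |

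With hazard ratio 2 and no true change, 10% drop-out gives −8% and −12%, and 30% gives −19% and −28%.

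**What removes the artefact.** In the same constant-rate scenarios, following the same subjects in every month gives 0%, as does keeping leavers in the mean at their own rate. The count model proposed under the fix targets this within-subject change; it was not itself simulated.

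**Why a fixed cohort alone is not enough.** Suppose 20% of subjects go from 0.5 to 1.0 in month 6 and leave in month 8. The all-available mean in months 6 and 7 is 0.8 × 0.5 + 0.2 × 1.0 = 0.60, a rise of 20%. A cohort restricted to those who reach Week 48 shows 0.5 throughout and misses that waning.

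**The case against.** The best defence is that this is a descriptive endpoint in an extension whose primary objectives concern safety, and that the SAP surrounds the curve with other information. Discontinuation for lack of efficacy is a secondary endpoint of its own, counted by Part (Section 8.7.5). Subjects who stop early are not counted as attack-free (Section 6.7.5.2). Exposure is shown by Kaplan-Meier plots (Section 10.2). Entire-study rate tables keep leavers' on-drug data. Section 6.4 puts the number with available data in every continuous summary. All of this is true and tells a reader that attrition occurred, but none of it separates within-subject change from composition in the monthly trend.

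By-month change from baseline is the nearest thing to an answer. It deals with differing pre-treatment rates but not with selection on response. If every subject had a pre-treatment rate of 1 (an assumption), the mean reduction in the first row of the working would still move from 50% to 62.5% with nobody changing.

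The SAP also does not say that the monthly plot decides durability; that role is inferred from the absence of any other analysis of the trend. Part 3 months restart at the first Part 3 dose, so earlier drop-out cannot create a trend inside that curve; only drop-out during Part 3 can.

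For AE-QoL, change from baseline by visit and the responder summary repeated at the end of the study are both planned. However, the Week 24 reference for former placebo subjects is their last value before active drug (Section 6.6, Table 8), not an on-drug visit.

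**Conclusion.** The point holds as a conditional one. Durability has no analysis beyond by-month means over subjects still on drug. If poorer responders leave more often, those means can hide waning or show improvement that no subject had. Under the assumed cases the false fall is 11% to 25% of the active rate; under graded dependence with 20% drop-out it is 8% to 29%.

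Three stronger readings are tempting, and the documents do not support them.

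- A reader might infer that the bias is certain and always favours the drug. It is zero when leaving is unrelated to rate. Table 13 also lists ineligibility, noncompliance, intercurrent illness, withdrawn consent, QT prolongation and rash, none of which by itself implies a poor response. If better responders left, the sign would reverse.
- A reader might take 20% as the expected attrition in Parts 2 and 3. It is an allowance made when sizing the groups, described there as conservative, and not a forecast for the extension.
- A reader might conclude that the numbers contributing are concealed, or that a cohort of those who reach Week 48 or 96 would settle the matter. The tables already carry the numbers, and such a cohort consists of completers.

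**What to change.** In Section 8.6.1:

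- Keep the all-available monthly curve and print the number contributing at each month on the figures.
- Add a repeated-measures count model on all on-drug 28-day months, with a log exposure offset, a subject effect and month. Report the within-subject month trend by dose, and name it as the analysis of durability.
- Model Part 3 separately, because its attacks are adjusted subject-reported events under different criteria (Section 6.7.5.1).
- If wanted, add fixed-cohort displays to Week 48 and Week 96 as a supplement, labelled as completers, with a note that they omit subjects who waned and then left.

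In Section 8.7.1, add within-subject change in AE-QoL from an early on-drug visit for every active group, not only former placebo subjects, with the number contributing.

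The cost is a few extra outputs from data already collected; no planned display is lost. The limit is that the model uses leavers' months on drug but still rests on assumptions about their unobserved later course, so the text should say so.
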